Environmental conditions (ambient OR temperatures, overhead lighting, electrical equipment), personal factors (personal protective equipment, metabolic heat, core and skin temperatures) and situational factors (type and length of a surgical procedure, perceived ergonomic workload) contribute to the presence of occupational heat stress experienced by surgeons performing surgical procedures. Surgeons' physiological and psychological responses to heat stress are measureable through a self-reported response to thermal comfort and perceived ergonomic workload, skin and core body temperature sensors, and a cognitive battery assessment. The physiological and psychological measure of surgeons' responses to heat stress can be influenced by wearing a cooling vest during the surgical procedure (Figure 1).

[figure not shown]

Figure 1. Conceptual Framework.

Methods

The trial will be conducted with Cleveland Clinic IRB approval and consent from participating surgeons. The trial will be registered at ClinicalTrials.gov. A full statistical analysis plan will be developed before any data are evaluated. Reporting will be consistent with the CONSORT guidelines.

Subject selection

Inclusion criteria are: 1) surgeons who perform elective major orthopedic surgery such as total hip and knee arthroplasties scheduled for 90 to 150 minutes at the Cleveland Clinic Main Campus; 2) Orthopedic surgeons ages of 25-65 years old, as body temperatures may be lower and less stable

in the elderly (Waalen & Buxbaum, 2011), who operate frequently enough to participate in four cross-over cases; 3) Surgical procedures in which surgical helmet systems or airborne barrier protection devices are worn are included as long as the surgeon wears the system for all four cases being measured.

Exclusion criteria are: 1) Surgical cases that require surgeons to sit on stools during the procedure, which may impact temperature and energy expenditure; 2) Surgeons who report having a recent illness within 24 hours prior to the surgery, symptoms producing a febrile condition; 3) Surgeons who worked the previous evening; and 4) Surgeons who wear lead X-ray gowns.

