Surgeon research subjects will be recruited by posting information about the study on the Orthopedic and Rheumatology Institute website. All human subject research protocols instituted by the Cleveland Clinic will be followed and documented. Participating surgeons will be advised of all known risks and benefits of study as well as information describing the requirements of the study and data management. The surgeons will be advised of the option to stop participation at any time. Written informed consent will be obtained from each surgeon.

Participating surgeons will be assigned a study number and only this number will be included on case-report forms. A single cross-linking record will identify specific surgeons for the purpose of organizing cross-over cases. Otherwise, analysis will be based on study number and no individual data will be linked to specific surgeons. Case-report forms will be kept locked in a secure research office and data-acquisition iPads will be encrypted.

We do not plan to obtain consent from patients for this comparative effectiveness trial that evaluates an FDA exempt device designed to improve *surgeons' comfort*.

Protocol

We propose a randomized cross-over trial using a uniform and strongly balanced 4-period design in which will include four operations for each surgeon. Surgeons will be randomized to 1 of 4 sequences: ABBA, BAAB, AABB or BBAA. The design is “uniform” in that each treatment appears the same number of times within each sequence (uniform within sequence) and if each treatment appears the same number of times within each period (uniform within each period). It is strongly balanced with respect to first-order carryover effects because each treatment precedes every other treatment, *including itself*, the same number of times.

We chose this design versus a parallel group design because 1) it removed the potential for confounding, even with a small sample size, as comparisons are made within subject, and not between subjects; 2) the design is very efficient since within-subject comparisons are correlated, obviating the need for a larger study which would also not be practical in this setting. Also, no differential carryover effect is expected in this study, removing one of the main concerns with crossover trials.

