Surgeons will be randomly assigned to use either the CoolSource™ cooling vest (worn between scrubs) and a conventional surgical gown for each of 4 surgeries. Sequence of treatments within surgeons will be randomized (ABBA, BAAB, AABB or BBAA), and determined using the PLAN procedure in SAS, such that each surgeon will wear vest and non-vest twice. The sequencing will not be shared with any study personnel. Allocation for each case will be concealed with a web-based system that will be accessed only shortly before surgery.

We will target an ambient temperature of $21^{\circ}\text{C} \pm 1^{\circ}\text{C}$, and try to maintain the same temperature of each of the four study cases for each surgeon. The CoolSource vest holds six reusable cooling packs

located bilaterally on the shoulders, angled flank along the base of the rib cage, and along each side of the spine, mid-back. The vest will be donned over hospital-issued scrubs after all temperature sensing devices have been applied and before surgical hand scrubbing. Surgeons will wear the vest throughout surgery, and for a few additional minutes while postoperative assessments are made (details below).

The weight of the disposable cooling vest is 1 kg which is evenly distributed over both shoulders. The cooling packs have an insulated cover to reduce condensation or sweating while seated inside the vest pocket. The flexible frozen reusable cooling packs will be inserted into each of the six pockets and the vest belt will be tied to hold the cooling packs securely. The disposable cooling vests will be discarded after each case, and the cooling packs returned to a freezer.

Measurements

A questionnaire detailing demographic information (age, height, weight, age, ethnicity, and education level) training level, specialty program, and estimated past case volume will be completed by participating surgeons before their first case.

Temperature of the freezer holding the cooling packs will be assessed before randomization to confirm that the temperature is <0°C.

Before every surgical case starts the time the surgeon dons the cooling vest and the time the surgeon dons the sterile surgical gown will be recorded.

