Participants' age, weight, height, and other continuous demographics and baseline characteristics will be summarized using descriptive statistics (n, mean, median, standard deviation, minimum and maximum), while race, surgical specialty, as well as other categorical variables will be summarized with frequency tabulations. The 4 sequence groups will be compared on baseline variables descriptively.

Specific Aim 1) Evaluate the difference between surgeons' self-rated thermal comfort with and without a cooling vest during prolonged and strenuous surgery. 0-10.

Perceived measure of thermal comfort for both conditions, with and without a cooling vest will be analyzed by descriptive statistics recommended for ordinal Likert scale items – i.e., frequencies and median [quartiles].

We will use a linear mixed effects model to test the treatment effect of the cooling vest on mean thermal comfort. We will adjust for treatment, sequence and period effects, and include subject as a random effect to account for the within-subject correlation. We will test for differential carryover effect by assessing the treatment-by-period interaction. If no interaction is detected the interaction term will be removed and the treatment effect assessed in a main effects model.

Specific Aim 2) Evaluate the difference between the surgeons' core, mean skin, and mean body temperatures with and without a cooling vest during a prolonged strenuous surgery.

For each temperature we will used a linear mixed effects model to test the treatment effect of the cooling vest on a subject's temperature during the case. We will adjust for treatment, sequence and period effects, and include subject as a random effect to account for the within-subject correlation. We will test for differential carryover effect by assessing the treatment-by-period interaction. If no interaction is detected the interaction term will be removed and the treatment effect assessed in a main effects model.

Specific Aim 3: Evaluate the difference between the surgeons' measure of cognitive performance with and without a cooling vest just after a prolonged strenuous surgery.

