Cognitive performance will be measured by the C3B performance-based battery of cognitive tests at the end of the case. An overall score for a subject after a particular case will be calculated by first rescaling (e.g., so that each item ranges from 0 to 100) and then averaging the scores across the battery. Treatment effect will be assessed using a linear mixed effects model as described for Aims 1 and 2.

The significance level will be 0.05 for the primary outcome (Aim 1) and 0.05 across the 3 secondary outcomes (2 temperatures, cognitive function), such that the secondary outcomes will be assessed at a significance criterion of $0.05/3=0.017$. SAS statistical software version 9.4, Carey, NC, will be used for all analyses.

Specific Aim 4: Evaluate the difference between the surgeons' perceived ergonomic workload with and without a cooling vest during a prolonged and strenuous surgery.

Perceived ergonomic workload will be measured by duration of the surgical procedure recorded in minutes, surgeons' report of the number of hours slept prior to the study day, Borgs' visual analog scale for exertion (0-10), and the Rating of fatigue scale (0-10).

Perceived ergonomic workload for both conditions, with and without a cooling vest will be analyzed by descriptive statistics recommended for ordinal measured items – i.e., frequencies and median [quartiles].

We will use a linear mixed effects model to test the treatment effect of the cooling vest on mean perceived levels of exertion and fatigue. We will adjust for treatment, sequence and period effects, and include subject as a random effect to account for the within-subject correlation. We will test for differential carryover effect by assessing the treatment-by-period interaction. If no interaction is detected the interaction term will be removed and the treatment effect assessed in a main effects model.

Sample Size Justification.

Sample size calculation is based on having 90% power at the 0.05 significance level to detect a difference of 2 or more (on a scale of 0-10) on surgeons' self-rated thermal comfort with and without a cooling vest. With an estimate SD (s) of 3 for thermal comfort in each group, and an assumed within-subject correlation (ρ) of 0.5, the estimated SD of the within-subject difference would be

$$\sqrt{s_1^2 + s_2^2 - 2\rho s_1 s_2}, \text{ or } \sqrt{2(3^2) - 2(0.5)(3)(3)} = 3.$$

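### The treatment models assume one common vest effect for all surgeons; if the effect varies between surgeons (the documents give no value), standard errors are too small

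*Combined protocol and SAP*

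**What the plan says.** Under Data Analysis, the models for Specific Aims 1, 2 and 4 contain fixed treatment, sequence and period effects and "include subject as a random effect to account for the within-subject correlation". Aim 3 adopts the same model by reference: "Treatment effect will be assessed using a linear mixed effects model as described for Aims 1 and 2". The only interaction considered is treatment-by-period, as a carryover check. No surgeon-by-treatment random effect, robust standard error or degrees-of-freedom method is given. The words intercept only do not appear, but a random intercept is what the text describes.

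The Protocol section sets the design: "Surgeons will be randomized to 1 of 4 sequences: ABBA, BAAB, AABB or BBAA", so that "each surgeon will wear vest and non-vest twice". Each surgeon therefore contributes replicate cases under both conditions.

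The primary test uses 0.05. For two temperatures and cognition, "the secondary outcomes will be assessed at a significance criterion of" 0.05/3 = 0.017. Aim 4 has no stated level.

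The Sample Size Justification works from one vest-minus-non-vest difference per surgeon: "the estimated SD of the within-subject difference would be" 3, leading to 26 surgeons. It also foresees a reassessment of variability after 13 surgeons.

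**The concern.** A random intercept makes all four cases of a surgeon equally correlated and gives every surgeon the same vest effect. The vest is then tested against pooled case-to-case error on about 74 df. If surgeons respond differently, the average effect should be judged against surgeon-to-surgeon variation in that effect, which has about 25 df or fewer. The pooled error contains only part of that variation, so intervals are too narrow and a test of zero average effect rejects too often.

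The sizing and the analysis also use different error terms. The sample size rests on surgeon-level differences, whose SD would include any variation in response. The analysis model leaves that variation out, although the two-plus-two replication is enough to estimate it.

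**Working it through.** **Inputs.** From the Sample Size Justification: SD 3 per condition, within-subject correlation 0.5, difference 2, power 90%, level 0.05, 26 surgeons. These imply a between-surgeon variance of 0.5 × 9 = 4.5 and a residual variance σ² = 9 − 4.5 = 4.5. From the Protocol section: four sequences, two cases per condition. Assumed here: the between-surgeon SD of the vest effect, s, from 0 to 2.5 points; two-sided testing; allocation 7/7/6/6.

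**The plan's own figure.** SD of a single-pair difference = √(9 + 9 − 2 × 0.5 × 3 × 3) = 3. A two-sided paired t-test for 2 points has power 0.904 with 26 surgeons and 0.892 with 25, so the stated 26 is reproduced. The detectable effect sizes, 0.66 at 0.05 and 0.76 at 0.017, also agree.

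**Correct error term.** A surgeon's mean difference (two vest cases against two non-vest cases) has variance σ²/2 + σ²/2 + s² = σ² + s². The true SE of the average effect is √((4.5 + s²)/26).

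**Error term in the planned model.** There are 26 × 3 = 78 within-surgeon df. Removing 1 for treatment and 3 for period leaves 74. About a third of these carry surgeon-to-surgeon differences in vest effect, so the pooled residual has expectation of about 4.5 + s²/3. The model SE is about √((4.5 + s²/3)/26).

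| s | True SE | Model SE | Ratio |
|---|---|---|---|
| 0 | √(4.50/26) = 0.416 | 0.416 | 1 |
| 0.5 | √(4.75/26) = 0.427 | √(4.58/26) = 0.420 | 0.98 |
| 1 | √(5.50/26) = 0.460 | √(4.83/26) = 0.431 | 0.94 |
| 1.5 | √(6.75/26) = 0.510 | √(5.25/26) = 0.449 | 0.88 |
| 2 | √(8.50/26) = 0.572 | √(5.83/26) = 0.474 | 0.83 |

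**Rejection rates under a zero average effect.** Simulating the four-sequence design (40,000 trials per setting, treatment and period fitted within surgeon) gives 4.8%, 5.4%, 6.7%, 8.4% and 10.3% at nominal 5% for s = 0, 0.5, 1, 1.5 and 2, and 12.5% at s = 2.5. REML fits of the random-intercept model (2,500 trials each) give 8.2% at s = 1.5 and 10.6% at s = 2. Rounded: about 5.4%, 7%, 8% and 10.5% for s = 0.5 to 2. A t-test on surgeon-level differences stays at 4.9% to 5.2% throughout.

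Interval coverage does not depend on the mean effect. A nominal 95% interval covers about 94.6%, 93%, 92% and 89.5% at s = 0.5, 1, 1.5 and 2.

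**At 0.017.** With the same variance ratios, simulation gives about 1.8%, 2.6%, 3.4% and 4.6% for s = 0.5, 1, 1.5 and 2. No variances are given for temperature or cognition, so these figures carry over only if s²/σ² is similar there.

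**Sensitivity to how s enters.** Above, s² is added to a residual variance of 4.5, so at s = 2 a single-pair difference has SD √(9 + 4) = 3.6. If that SD is instead held at the plan's 3, the residual variance is (9 − s²)/2, and the 5% test rejects 5.3%, 7.0%, 9.6% and 13.4% for s = 0.5, 1, 1.5 and 2.

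**Power after the change.** Noncentral t, 2 points, 26 surgeons, SD √(4.5 + s²): about 99% at s = 1, 97% at 1.5, 92% at 2 and 85% at 2.5. The stated power survives because the plan budgeted a variance of 9 per surgeon. The surgeon-level variance 4.5 + s² reaches 9 only at s = √4.5 = 2.1.

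**The case against.** The strongest reply is that everything depends on s, which the documents do not give. That stands. At s = 0.5 the inflation is negligible. If the vest does nothing for any surgeon, then s = 0 and the planned test holds its level. The rejection figures need a zero average effect combined with sizeable opposite individual effects, which is a narrow scenario for a vest holding frozen packs. At a true 2-point effect, the planned and surgeon-level tests disagree on significance in only 0.7%, 1.7% and 4.6% of simulated trials (s = 1, 1.5, 2). The primary conclusion would rarely change. The undercoverage of the interval does not go away, though, because it does not depend on the mean effect.

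Several stronger readings are tempting but unsupported:

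- A reader might infer that the primary test does run at 7–10%. That range applies only if s is about 1 to 2 points.
- A reader might take variation in response as shown, since ages run from 25 to 65 and "Surgical procedures in which surgical helmet systems or airborne barrier protection devices are worn are included". These permit differences between surgeons; nothing in the documents shows that either factor changes the response to the vest.
- A reader might infer false-positive rates above 5% for the secondary outcomes as well. Those tested at 0.017 stay below 5% up to s = 2, and Aim 4 has no level to exceed.
- A reader might infer that 26 surgeons is wrong. It reproduces.
- A reader might suppose that the change never takes power below 90%. At s = 2.5 it does.

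It can also be said that a full analysis plan is promised before data are evaluated and could add the term. It could, but the model now written does not contain it.

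**Conclusion.** The point holds conditionally. As written, the models for Aims 1–4 assume a vest effect common to all surgeons, and their standard errors are too small if that is untrue. The excess is trivial at s = 0.5. At s = 2 the primary test's type I error roughly doubles, with the model SE at about 83% of its true value. These sizes rest on the plan's comfort-scale variances, 26 surgeons with complete data and an assumed s; they are not estimates of what this trial will show. Relative inflation is greater at 0.017 than at 0.05, but over the same range the absolute rates stay under 5%. This is an inexpensive improvement to the pre-specified analysis; it does not invalidate the design or the sample size.

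**What to change.** Pre-specify one period-adjusted analysis for all four aims, in either of two essentially equivalent forms:

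- add a random surgeon-by-vest term to the stated mixed model, with Kenward-Roger degrees of freedom; or
- regress each surgeon's mean vest-minus-non-vest difference on an intercept and the two period contrasts implied by sequence (+1/−1 for ABBA/BAAB and for AABB/BBAA), leaving 26 − 3 = 23 df.

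Choose one now and use it whatever the variance estimate turns out to be, with no switch when that estimate is zero. The surgeon-level regression meets this most simply, because its error term does not depend on an estimated variance component.

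Do not substitute an unadjusted paired test. In AABB and BBAA a time trend enters each surgeon's difference. At s = 2, a trend of 1 point per period lowers that test's power for 2 points from about 92% to about 88%. This matters especially for cognition, where the Measurements section itself anticipates learning.

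Use the same surgeon-level variance in the reassessment after 13 surgeons. The random-intercept residual would target about 4.5 + s²/3 instead of 4.5 + s² (5.83 against 8.5 at s = 2).

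The cost is one RANDOM term in SAS or a short regression, fewer df, and slightly wider intervals if response does not vary. No new data are needed. Power for 2 points falls below the stated 90% only if s exceeds about 2.1.

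### The treatment-by-period interaction picks up only about 9% of additive first-order carryover in these four sequences, so it cannot serve as the carryover test

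*Combined protocol and SAP*

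**What the plan says.** Under Protocol, the design is four operations per surgeon: "Surgeons will be randomized to 1 of 4 sequences: ABBA, BAAB, AABB or BBAA". The stated merit is balance: "It is strongly balanced with respect to first-order carryover effects because each treatment precedes every other treatment", itself included. The same section adds that "no differential carryover effect is expected in this study" and counts this in favour of a crossover. The sequence is "determined using the PLAN procedure in SAS, such that each surgeon will wear vest and non-vest twice". Neither blocking nor equal numbers per sequence is stated.

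Under Data Analysis, Specific Aim 1, a linear mixed model with treatment, sequence, period and a random surgeon effect will "test the treatment effect of the cooling vest on mean thermal comfort". Carryover is handled in two sentences: "We will test for differential carryover effect by assessing the treatment-by-period interaction", then "If no interaction is detected the interaction term will be removed and the treatment effect assessed in a main effects model". Aims 2 and 4 repeat this. For Aim 3, "Treatment effect will be assessed using a linear mixed effects model as described for Aims 1 and 2".

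No term for the preceding condition is specified. No significance level is given for the interaction, and no action is given if an interaction is found. Subject selection asks for enough operating volume to supply four cases but sets no minimum interval between them.

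**The concern.** First-order carryover here means that the condition worn in a surgeon's preceding study case affects the rating in the current one. In some crossover designs the treatment-by-period interaction is a workable stand-in for it. In a strongly balanced design it is not, because the balance that protects the vest estimate also removes the carryover signal from the treatment-by-period cell means.

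The plan uses this interaction as its only check on a stated design assumption, and lets the result choose the final model. A non-significant interaction would naturally be reported as no differential carryover, and the data could hardly support that statement. The documents describe no washout interval that would make the check unnecessary.

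**Working it through.** **Inputs.** Sequences from Protocol. From Sample Size Justification: SD 3, within-surgeon correlation 0.5, 26 surgeons, 2-point target. Within-surgeon variance = 9 × (1 − 0.5) = 4.5. Assumed: complete data, period as a four-level factor, 5% level for the carryover test.

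**Plan's own figure.** A paired t-test with effect size 2/3 and two-sided 5% has power 0.892 at n = 25 and 0.904 at n = 26. The stated 26 is reproduced.

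**Share captured, one surgeon per sequence.** Code A = +1 and B = −1. The carryover code is the preceding case's code, and 0 in case 1.

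1. Raw sum of squares: 4 × 3 = 12.
2. Surgeon means of the code are −1/4 (ABBA), +1/4 (BAAB), +1/4 (AABB) and −1/4 (BBAA). They remove 4 × 4 × (1/16) = 1. Period and treatment remove nothing, since transitions AA, AB, BA and BB occur three times each and are balanced within each period. Adjusted sum of squares: 11.
3. Before surgeon adjustment, the mean carryover code is 0 under A and under B in every period. After it, the code has inner products 0, −1, 0 and +1 with the treatment code in periods 1 to 4. Only the period-4 minus period-2 contrast of the treatment effect is touched. Its inner product with carryover is 2 and its own adjusted sum of squares is 8 − 4 = 4, so it captures 2²/4 = 1.
4. Share = 1/11 = 9.1%. Across the 7/7/6/6 splits it is 9.05% to 9.6%. With period as a linear trend it is 3.0%.

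**Power, 26 surgeons split 7/7/6/6.** Residual df: 104 − 26 − 3 − 1 = 74, leaving 71 with the 3-df interaction and 73 with the 1-df previous-condition term. Simulation, 20,000 runs per scenario:

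| Additive first-order difference (points) | Interaction | Previous-condition term |
|---|---|---|
| 0.5 | 5% | 17% |
| 1 | 6% | 50% |
| 1.5 | 7% | 84% |
| 2 | 9% | 97–98% |

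A non-significant interaction has probability about 0.91 with 2-point carryover and 0.95 with none, a ratio of 0.91/0.95 = 0.96.

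**Precision of the direct term.** With adjusted sum of squares 71.46, the SE of the A-minus-B carryover difference is 2 × √(4.5/71.46) = 0.50. The 95% CI half-width on 73 df is 1.0 point.

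**Effect on the vest estimate, additive first-order, 2 points.** The shift is 0 with equal sequences and 0 to 0.04 at 7/7/6/6. If sequence sizes are left to simple randomisation (assumed), the median shift is 0.07 and the 97.5th percentile 0.22; power is then 12% for the interaction against 97% for the direct term.

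**Other forms of carryover.**

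- *Vest case into a following no-vest case only.* Three of every eight no-vest cases follow a vest case, so the vest effect moves toward zero by 3/8 = 0.375 points per point with equal sequences (0.365 to 0.385 at 7/7/6/6). Adding the term barely changes this (0.365 to 0.384). Power at 2 points: interaction 8–10%, previous-condition term 48–50%.
- *Second-order (condition two cases back).* In all four sequences case 3 is the opposite of case 1, and case 4 the opposite of case 2. This form is therefore fully aliased with a vest effect that changes over cases, and the interaction captures 100% of it. At 2 points the vest effect shifts by 1.0 point with or without the term. Power: interaction 25–27%, previous-condition term about 6%.
- *Halving with each case, or equal cumulative carryover.* The interaction captures about 4% and 0% to 0.6%. The vest effect shifts by 0.25 and 0.5 points per point, entirely through the second-order component.

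**The case against.** The strongest reply is that strong balance was chosen so that first-order carryover would not distort the vest effect, and it works: a carryover as large as the 2-point target moves the estimate by at most 0.04 at near-equal sequence sizes. This stands, and it limits the consequence. It depends, however, on near-equal sequences, which the plan does not state, and it does not rescue the carryover conclusion itself.

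Second, the interaction is the better detector of second-order carryover, which does bias the estimate. This also stands, and is why the interaction should be kept. It cannot separate that form from a vest effect that changes over cases, so a descriptive role suits it.

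Third, carryover of 1 or 2 points is hypothetical. The plan expects none, vests are discarded, and packs go back to the freezer after each case. At 0.5 points the direct term is weak too, and its CI half-width of 1.0 point cannot rule out small carryover. That is true, and it argues for reporting an estimate with its interval rather than a p-value.

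Finally, the plan does not literally say it will conclude that carryover is absent, and Methods promises a complete SAP before the data are examined. Calling the interaction a test of carryover makes that conclusion the natural reading, and the promised SAP is the place to correct it.

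**Conclusion.** The concern holds. The planned test does not do its stated job in this design: it captures 1/11 of additive first-order carryover and has about 9% power at 2 points, against 97–98% for a direct term. The power figures rest on the plan's SD and correlation, 26 complete surgeons, a four-level period factor and an assumed 5% level; the 1/11 depends only on the sequences and the factor coding.

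The consequence is modest. The defect lies in what a non-significant result can support, with little effect on the primary estimate under additive first-order carryover and near-equal sequences. That protection does not extend to vest-to-no-vest or second-order carryover. It is worth changing because the change is nearly free. The missing action for a detected interaction is a smaller gap that the same change closes.

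**What to change.** In the full SAP, for all four aims:

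1. Assess carryover with a first-order term: condition worn in the surgeon's preceding study case, zero for case 1. Report its estimate and 95% CI.
2. Take the period-averaged vest effect from one prespecified model, whatever the carryover or interaction result, with no pretest. The model may include the carryover term or not, provided this is fixed in advance. Including it is safer unless sequence sizes are forced near-equal, because it removes the additive first-order shift.
3. Keep treatment-by-period as a descriptive check of whether the vest effect changes over cases, noting that second-order carryover would look the same.
4. State that the added term does not correct the vest effect for carryover confined to no-vest cases after a vest case, or for second-order carryover, including the second-order part of decaying or cumulative patterns.

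Cost: one degree of freedom, two or three sentences and no new data. The variance of the vest effect rises by 0% to 0.05% at 7/7/6/6; under simple randomisation the median is 0.2% and the 95th percentile 1.4%.
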